15.5 Other Safety or Tolerability Evaluations

ECG

Single 12-lead ECGs will be obtained at screening and repeated during the study if clinically indicated using an ECG machine that automatically calculates the heart rate and measures PR, QRS, QT, QTc Intervals, and ECG parameters will be derived from the data collected on the “Electrocardiogram” eCRF page.

A listing of ECG values will be provided including participant identifier, age, sex, race, ECG parameter and unit, visit, ECG date, value, change from baseline. Baseline values and post-baseline values collected after the on-treatment period will be flagged. Qualitative ECG results will also be provided in the listing.

ECOG Performance Status (ECOG PS)

The ECOG PS will be derived from the data collected on the “ECOG Performance Status” eCRF page.

The ECOG shift from baseline to the highest score during the on-treatment period will be summarized.

ECOG PS will also be presented in a listing at each timepoint.

16 Analyses of Other Endpoints

16.1 Pharmacokinetics

The analyses described in this section will be performed by the Clinical PK/PD group (CPK) of Translational Medicine, Merck Healthcare KGaA, Darmstadt, Germany, or by a Contract Research Organization selected by the Sponsor. Pharmacokinetic listings and individual data will be presented based on the SAF. Summaries and statistical analyses will be based on the PKAS.

Pharmacokinetic concentrations/parameters refer to bintrafusp alfa concentrations/PK parameters.

16.1.1 Missing/non-quantifiable PK Data Handling

Concentrations below the lower limit of assay quantification

Pharmacokinetic concentrations below the lower limit of quantification will be set to zero for calculating parameters and descriptive statistics.

Deviations, missing concentrations, and anomalous values

There will be no imputation of missing data. Concentrations will be set to missing in summary tables if the value is reported as no result. Pharmacokinetic concentrations which are erroneous due to a protocol violation or event (as defined in section 10.2) may be excluded from the PK analysis if agreed upon prior to performing a statistical analysis. Any other PK concentrations that appear implausible to the Pharmacokineticist/PK Data Analyst must not be excluded from the analysis. Any implausible data will be documented in the CSR.

If a PK parameter cannot be derived from a participant's concentration data, the parameter will be coded as NC (not calculated). (Note that NC values will not be generated beyond the day that a participant discontinues the treatment). For statistical analyses, PK parameters coded as NC will be set to missing.

If an individual participant has a known biased estimate of a PK parameter (due for example to a deviation from the assigned dose level), this participant/value will be excluded from the descriptive statistics, and instead the result will be listed in a separate table.

Relevant decisions on participant inclusion in the PKAS will be made before database lock in the Database Review Meeting (DRM).

16.1.2 Descriptive PK Analysis

Presentation of PK Concentration Data

A by-participant listing will present PK sample times, time deviations, and concentrations based on the SAF. Concentrations will be reported with the same precision as the source data.

Presentation of PK Parameter Data

The PK parameters listed below will be taken directly from the observed bintrafusp alfa concentration-time data.

C_{trough} The concentration observed immediately before next dosing (corresponding to pre-dose or trough concentration for multiple dosing).

C_{EOI} The concentration observed immediately at the end of infusion.

Individual PK parameters will be listed by nominal study day based on the SAF. Individual PK parameters will be reported with the same precision as the source data.

Pharmacokinetic parameter data will be presented in tables and descriptively summarized by nominal study day using: n, Mean, StD, coefficient of variation (CV%), Min, Med, Max, geometric mean (GeoMean), the geometric coefficient of variation (GeoCV) and the 95% CI for the GeoMean (LCL 95% GM, UCL 95% GM). Summaries will be based on the PKAS.

Additional table(s) will summarize with further stratification by ADA subsets ever positive and never positive.

In export datasets (e.g. from WinNonlin®), as well as in the SDTM PP domain, PK parameters will be provided with full precision and will not be rounded. Descriptive statistics of PK parameter data will be calculated using full precision values and rounded for reporting purposes only.

The following conventions will be applied when reporting descriptive statistics of PK parameter data:

- Mean, Min, Med, Max, GeoMean, 95% CI: 3 significant digits
- StD: 4 significant digits
- CV%, GeoCV%: 1 decimal place

Individual PK C_{trough} and C_{EOI} values will be plotted versus actual study day on a linear scale, for all participants. Individual data will be presented based on the SAF.

Arithmetic mean (\pm StD) and median C_{trough} and C_{EOI} will be plotted versus nominal study day on a linear scale. Summaries will be based on the PKAS.

Additional figure(s) will be presented with further stratification by ADA subsets ever positive and never positive as long as both subsets consist of 5 or more participants.

16.2 Pharmacodynamics

Not applicable.

16.3 Immunogenicity

Analysis Sets: IMM

The ADA results will be derived for each visit based on the algorithm in Table 14.

Table 14 Algorithm for the Derivation of ADA Results

Sample Screen Result	Confirmatory	Titer	ADA Result
Negative	NA	NA	Negative
NR	NA	NA	NR
Positive	Negative	NA	Negative
Positive	NR	NA	NR
Positive	Positive	Number	Number
Positive	Positive	NR	Positive-TNR

NR = no result, NA = not applicable, TNR = titer no result.

Note that samples collected during and after the on-treatment period (e.g. safety follow-up) including the ones collected during the reinitiation period will be included in the analysis. Negative, number, or positive-TNR are valid results while number and positive-TNR are considered as positive. Participants will be characterized into different categories based on the criteria in Table 15.

Table 15 Participants Characterized based on ADA Results

Category	Definition	Participant at Risk (Denominator for Incidence)
Never positive	No positive results at any time point	Number of participants with at least one valid result at any time point
Ever positive	At least one positive result at any time point, including baseline	Number of participants with at least one valid result at any time point
Pre-existing	A positive ADA result prior to treatment with bintrafusp alfa	Number of participants with valid baseline result
Treatment boosted	A positive ADA result prior to treatment with bintrafusp alfa and at least one post-baseline value with ADA titer result $\geq 8^{\circ}$ baseline ADA titer result	Number of participants with valid baseline result and at least one valid post-baseline result
Treatment emergent	Not positive prior to treatment with bintrafusp alfa and with at least one positive post-baseline result	Number of participants with at least one valid post-baseline result and without positive baseline result (including missing, NR)
Transient positive	If treatment emergent participants have: - a single positive evaluation and last assessment not positive or - duration between first and last positive result < 16 weeks and last assessment not positive	Number of participants with at least one valid post-baseline result and without positive baseline result (including missing, NR)
Persistent positive	If treatment emergent participants have duration between first and last positive result ≥ 16 weeks or a positive evaluation at the last assessment	Number of participants with at least one valid post-baseline result and without positive baseline result (including missing, NR)

[figure not shown]
The following analysis will be described:

- The frequency and percentage of each ADA category, as defined in [Table 15](#), will be tabulated
- Evaluation of potential effect of ADA status on bintralusp alfa safety (see section [15.1.1](#))
- Evaluation of potential effect of ADA status on bintralusp alfa efficacy
 - for best overall response according to RECIST 1.1 as adjudicated by IRC (see section [14.1.1](#))
 - for progression-free survival according to RECIST 1.1 as adjudicated by IRC (see section [14.4](#))
 - for overall survival (see section [14.7](#))

Potential effect of ADA on safety and efficacy will be evaluated on ADA positive status (ever positive, never positive).

A listing of ADA results from ever positive participants will be provided with the following: participant ID, age, sex, race, ADA categories status, visit, date of assessment and results of screening, confirmatory and titer values.

CCI

17

References

18 Appendices

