PK and ADA sampling		See Table 2 for PK and ADA sampling times																		
Whole blood for pharmacogenetics			X															Whole blood sample for participants who provide separate informed consent. This sample can be collected at any other visit if missed in this visit.		
Liquid biopsy (plasma)			X	X						X		Q12W	X					Liquid biopsy (plasma) for genetic profiling including TMB analysis will be collected within 2 hours prior to study intervention infusion as scheduled.		

ADA=antidrug antibody, AE=adverse events, β -hCG= β -human chorionic gonadotropin, CT=computed tomography, D=Day, ECG=electrocardiogram, ECOG PS=Eastern Cooperative Oncology Group performance status, FSH=follicle-stimulating hormone, HBV=hepatitis B virus, HCV=hepatitis C virus, HIV=Human immunodeficiency virus, HMGA2=High Mobility Group AT-Hook 2, ICF= informed consent form, MRI=magnetic resonance imaging, PD=progressive disease, PE=physical examination, PK=pharmacokinetics, Q2W=every 2 weeks; Q4W=every 4 weeks, Q6W=every 6 weeks, Q8W=every 8 weeks, Q12W=every 12 weeks, T4=free thyroxine, TMB= Tumor mutational burden, TSH=thyroid-stimulating hormone, V=visit, W=Week.

Table 2

Bintrafusp alfa Pharmacokinetic, Immunogenicity Sampling

Bintrafusp alfa Measure	Screening / Baseline Assessments	Intervention Period (\pm 3 days)					End-of- Treatment Visit	Safety Follow-up Visit		Notes	
		V1	V2	V3	V4	V7		Up to 28 Days (\pm 5 days) After Last Treatment	12 Weeks (\pm 2 weeks) After Last Treatment		
	Day -28 to First Treatment	V1	W3	W5	W7	W13	Until Progression Pre/End Infusion	On the Day of or Within 7 Days of Decision to Discontinue			
		D1 Pre/End Infusion	D15 Pre/End Infusion	D29 Pre/End Infusion	D43 Pre/End Infusion	D85 Pre/End Infusion					
Blood sample for PK		X/X	X/-	X/X	X/-	X/-	X/- Q6W up to/including W25, then Q12W	X	X	Samples for PK analysis to be taken before (pre) infusion (as close to the start of the infusion as possible), immediately after the completion of infusion (as close to the completion as possible but no later than 30 minutes post end of infusion). The predose sample should still be drawn even if dosing is ultimately deferred at the study visit. The exact time of each draw must be recorded.	
Blood sample for ADA		X/-	X/-	X/-	X/-	X/-	X/- Q6W up to/including W25, then Q12W	X	X	Predose ADA samples to be collected prior to study intervention infusions. The exact time of each draw must be recorded.	

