Approximately 20% of TNBC tumors express PD-L1, although expression is predominantly localized to the tumor-infiltrating lymphocytes ([Mittendorf 2014](#)). Importantly, in the TNBC cohort of the Phase I Study of the anti-PD-L1 drug, atezolizumab, higher PD-L1 expression correlated with improved response to treatment and survival ([Emens 2019](#)). Similarly, in the recent IMPassion130 study of nab-paclitaxel \pm atezolizumab in advanced, treatment-naïve TNBC, 40.9% of participants were determined to be PD-L1 positive and median overall survival (OS) was significantly improved in participants who received chemotherapy plus atezolizumab versus chemotherapy and placebo (25.0 months versus 18.0 months), highlighting the significant contribution of PD-L1 blockade for these participants ([Schmid 2018](#), [Schmid 2019](#)).

Bintrafusp alfa has shown promising clinical activity in participants with TNBC in the expansion cohort of the Phase I Study EMR200647-001 ([Spira 2019](#)). As of 15 October 2019, participants (n= 33) with heavily pretreated TNBC (54.5% of participants had ≥ 4 prior regimens) received a median of 3 (range 1 to 24) doses of bintrafusp alfa (1200 mg every 2 weeks). Responses as assessed by Investigator occurred in 4 participants; 3 of 4 responses were confirmed by Independent Review Committee (IRC), while the fourth was considered stable disease (SD). The objective response rate (ORR) for these 4 responses was 12.1% (95% confidence interval [CI]: 3.4, 28.2) and disease control was achieved in a total of 5 participants (15.2% [95% CI: 5.1, 31.9]) per Investigator. The median OS was 7.8 months (95% CI: 2.1, 12.8). PD-L1 expression in tumor cells or in the tumor microenvironment was not associated with response to treatment. Bintrafusp alfa was well tolerated, with a safety profile consistent with expectations in this heavily pretreated, advanced TNBC cohort.

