- Drug must not be given to a known pregnant participant (see Appendix 3).
- Use of a prohibited concomitant drug, as defined in Section 6.5.2, where the predefined consequence is withdrawal from the study intervention.

In case of discontinuation from the study intervention:

- The day of End-of-Treatment Visit will correspond to the day of withdrawal (or within 7 days).
- An attempt should be made to perform all assessments scheduled for the End-of-Treatment Visit if possible. If not possible, the most clinically relevant assessments and appropriate eCRFs for the End-of-Treatment Visit should be prioritized as feasible.
- Participants will be asked to continue Safety Follow-up and Survival Follow-up, which includes the collection of data on survival, and subsequent anticancer therapy. After completion of the follow-up period or after the End-of-Treatment Visit, whichever is applicable, the appropriate eCRF section for Study Termination must be completed.
- If the participant is enrolled into a new study or any new therapy post-withdrawal from study intervention, the Safety Follow-up Visit should be scheduled prior to the start of the new treatment irrespective of the 28-day Safety Follow-up period.

The Schedule of Activities specifies the data to collect at study intervention discontinuation and follow-up, and any additional evaluations that need to be completed.

7.1.1 **Temporary Discontinuation**

See Section 6.8 and Section 6.9 for guidance on temporary discontinuation from study intervention.

7.1.2 **Rechallenge**

7.1.2.1 **Reinitiation**

One reinitiating course of treatment at the same dose and schedule and treatment duration up to 24 months is allowed at the discretion of the Investigator and agreement of the Medical Responsible for:

- Participants who are experiencing SD, PR, or CR at the time of discontinuation, and then subsequently develop disease progression after stopping therapy, but prior to the End of the Study.

OR

- Participants who are discontinued due to an AE that are subsequently well managed or resolved after stopping therapy, but prior to the End of the Study.

The participant should reinitiate treatment at the treatment phase visit where they left off according to the Schedule of Activities (Table 1). Participants who reinitiate treatment should stay on study and should be treated and monitored according the Schedule of Activities for the rest of the study.

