8.2 Subgroup Definition and Parameterization

Subgroup analyses may be performed on primary and key secondary efficacy endpoints as defined below. All subgroup analyses will be exploratory and no adjustment for multiplicity will be performed.

For the definition of subgroup level, data as documented in the electronic case report form (eCRF) will be taken. The category “missing” will not be included in any subgroup analysis.

In case of low number of participants within a category (<5 participants), categories will be pooled when meaningful. Subgroup analyses will be omitted where pooling would result in only one remaining category.

The following subgroups will be defined:

- Age: < 65 years (reference level) / ≥ 65 years
- Number of prior treatment lines (neoadjuvant, adjuvant or metastatic/locally advanced prior anti-cancer drug therapies): 0 (reference level) / 1 / 2 / 3 / ≥ 4
- ADA status: Ever positive (reference level) / Never positive
- PD-L1 expression at baseline: negative (reference level) / positive / not evaluable
- Race: White (reference level) / Asian / Black / others **
- ECOG at day 1 PS 0 (reference level) / 1 / >1
- Prior treatment: Taxane yes (reference level) / no
- Prior treatment: Anthracycline yes (reference level) / no
- Prior treatment: Radiotherapy yes (reference level) / no
- Prior treatment: Neoadjuvant or adjuvant yes (reference level) / no
- Number of metastatic site: 0-3 (reference level) / >=4
- Site of metastatic disease Lung No (reference level) / yes
- Site of metastatic disease Liver No (reference level) / yes

- Site of metastatic disease Bone No (reference level) / yes
- Site of metastatic disease Brain No (reference level) / yes

** In case of race subgroups, the following categorization of the data collected in the eCRF will be applied:

- White: “White”
- Asian: “Asian”
- Black: “Black or African American”
- Others: “American Indian or Alaska Native”, “Native Hawaiian or Other Pacific Islander”, “Other”, “More than one race”
- Note that records marked as “Not collected at this site” in eCRF will be treated as missing race

9 General Specifications for Data Analyses

This section describes any general specifications not included in subsequent sections.

The “start date” for this study is the start date of treatment.

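### Does the ever versus never ADA-positive comparison need changing because status depends on time on treatment?

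*SAP*

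**What the plan says.** SAP 16.3 sets the comparison: "Potential effect of ADA on safety and efficacy will be evaluated on ADA positive status (ever positive, never positive". It names best overall response, PFS and OS for efficacy, and points to SAP 15.1.1 for safety, where the TEAE overview is repeated by ADA status. Table 15 defines ever positive as "At least one positive result at any time point, including baseline". Samples taken during and after treatment count, "including the ones collected during the reinitiation period will be included in the analysis". Protocol 7.1.2.1 opens reinitiation after stable disease or response, and also to "Participants who are discontinued due to an AE that are subsequently well managed or resolved after stopping therapy".

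SAP 8.2 lists "ADA status: Ever positive (reference level) / Never positive" among the efficacy subgroups, which SAP 14.1.2 applies to response. Section 8.2 calls subgroup analyses optional and exploratory and adds: "In case of low number of participants within a category (<5 participants), categories will be pooled when meaningful". It omits the analysis if pooling would leave one category.

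PFS (SAP 14.4) and OS (SAP 14.7) are timed from first dose. The TEAE window (SAP 9.8) closes 30 days after the last dose or at subsequent anticancer therapy, among other limits. No landmark, time-dependent or exposure-adjusted method is given.

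SAP 4.1, added in version 2.0 after the decision to stop the study early, says that efficacy, PK, immunogenicity and biomarker analyses will not be done. Other endpoints receive listings instead of summary tables as deemed appropriate, in an abbreviated report.

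**The concern.** The grouping variable is partly determined by what happens after time zero. To be classed positive after baseline, a participant must stay alive and in sampling long enough to seroconvert and be tested. Someone who progresses after one or two doses has few chances; a responder treated for a year has many.

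Even if antibodies did nothing, the ever-positive group would then hold more responders, longer PFS and OS and, because the TEAE window also lengthens with treatment, more participants with an event. Read at face value, such a table could hide a real loss of efficacy from antibodies or suggest a safety signal that is not there. Exposure can vary widely: participants in the earlier TNBC cohort (Protocol 2.2) "received a median of 3 (range 1 to 24) doses of bintrafusp alfa".

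**Working it through.** **Plan figures.** The documents give no ADA incidence, onset time or precision target, so there is no ADA figure to reproduce. The one design figure, 81% with 29 participants, reproduces: the exact lower limit passes 10% at 7 of 29 responses (10.3%; 6 of 29 gives 8.0%), and P(X ≥ 7 | n = 29, p = 0.30) = 81.2%. ADA status plays no part in it.

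**Step 1: samples by exposure.** Protocol Table 2 takes predose samples at D1, D15, D29, D43 and D85, then "Q6W up to/including W25, then Q12W", plus end of treatment and 28 days after the last dose. Scheduled post-baseline samples are:
- 1 dose: end of treatment and 28-day = 2.
- 3 doses (last D29): D15, D29, end of treatment, 28-day = 4.
- 24 doses (last D1 + 23 × 14 days, i.e. D323 by visit numbering): D15, D29, D43, D85, D127, D169, D253, end of treatment, 28-day = 9.

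If each sample had an independent chance p of being positive (assumed, and simplistic for antibodies), P(ever positive) = 1 − (1 − p)^k.

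| p | k = 2 | k = 4 | k = 9 |
|---|---|---|---|
| 5% | 10% | 19% | 37% |
| 10% | 19% | 34% | 61% |

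So the direction of the concern is right.

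**Step 2: size with no ADA effect, by onset time.** Null simulation with 30% response and 50% of participants able to form ADA. Assumed: PFS median 40 weeks in responders and 8 weeks in non-responders, post-progression survival median 16 weeks, constant TEAE hazard.

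| Median ADA onset | ORR, ever vs never | TEAE, ever vs never |
|---|---|---|
| 0.5 week | 30.7% vs 29.2% | 42.1% vs 40.6% |
| 12 weeks | 45.0% vs 24.1% | 54.2% vs 36.6% |
| 52 weeks | 56.6% vs 26.6% | 62.4% vs 38.7% |

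With baseline positives only, ORR is 29.6% vs 30.1%: no bias.

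**Step 3: size by share able to form ADA.** A second null model also uses 30% response, with assumed non-responder median progression of 2 months, a median of 9 doses, and exponential ADA onset with mean 3 to 12 months.

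| Share able to form ADA | ORR, ever vs never |
|---|---|
| 100% | 37–49% vs 6–19% |
| 50% | 37–48% vs 25–26% |
| 20% | 37–48% vs 28–29% |

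The widest gaps need every participant to be capable of seroconverting. At lower shares the never-positive group returns towards the overall rate and the ever-positive group becomes small.

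**Step 4: would the table exist?** With true ever-positive proportions of 10%, 12%, 20% and 30%, the binomial chance of fewer than 5 positives among 29 is 84%, 74%, 28% and 4%. At low incidence the small-category rule in SAP 8.2 would usually remove the efficacy subgroup.

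**Step 5: what the alternatives buy.**
- *Day-43 landmark.* Even if everyone can seroconvert, 2 to 11 of 29 are expected positive by then. The chance of fewer than 5 is 1–14%, 28–66% or 81–95% for mean onset of 3, 6 or 12 months. In a model set to the earlier cohort (median 3 doses, ORR 12.1%, median OS 7.8 months), 54% stop before the D43 predose sample. Keeping them leaves null gaps of 1–4 points; requiring a valid D43 result cuts the gaps to 0.5 points or less but drops that 54%.
- *Exposure-adjusted TEAE rates.* These balance (0.10 vs 0.10 per month) only if the rate is constant. With 0.20 per month for two months and 0.05 after (assumed), they become 0.09–0.12 in ever positive vs 0.12–0.18 in never positive, so the bias reverses.
- *Baseline (pre-existing) status.* Unbiased by time on treatment, but it does not address antibodies induced by the drug.

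**The case for a change.** The best case for amending is that the text of SAP 16.3 and 15.1.1 remains in the current version despite the cancellation. SAP 4.1 names efficacy and immunogenicity outright, whereas the TEAE table by ADA status belongs to safety, where tables give way to listings only as deemed appropriate. The exploratory label and the minimum of five belong to SAP 8.2 and are not repeated in 16.3 or 15.1.1, although SAP 16.1.2 sets its own minimum for the PK figures by ADA. An exploratory label does not remove a bias of known direction. The ADA listing and the two-week flag around positive samples in SAP 15.1.1 show timing but correct nothing. A landmark can also work: in the first simulation above, fixing status at week 6 among participants still progression-free gave ORR of about 42% in both groups and PFS event-rate ratios of 0.97 to 1.01.

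The mechanism, its direction and the absence of any adjustment all stand. So does the point that the TEAE table is dropped in effect and not by name. The step to a required change does not. No test, model or decision attaches to the split, and SAP 4.1 gives the small number of participants as the reason for using listings. The landmark result is a large-sample property and does not supply the positives that 29 participants may lack.

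**Conclusion.** The bias is genuine in principle, but no change to the plan is warranted because nothing would be gained. SAP 4.1 removes the efficacy and immunogenicity analyses and moves safety to listings as appropriate. The primary and secondary estimates and the Table 15 frequencies never depended on the ever/never split.

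Its size cannot be fixed from the documents. It is none for baseline positives, about 1.5 points of ORR for very early onset (30.7% − 29.2%), and 30 points for late onset (56.6% − 26.6%) with half of participants able to form ADA. It depends on both onset time and the share forming ADA, and neither is given. The simulations also leave out reinitiation and treatment beyond progression.

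At 29 participants the alternatives exchange one weakness for another: too few positives, more than half of participants dropped, or a TEAE comparison biased the other way. The dated ADA listing and the AE and infusion-reaction listings for ever-positive participants already specified in SAP 16.3 and 15.1.1 are a reasonable basis for individual review. Were an ever/never table produced after all, an analyst would read it as descriptive, since status depends on length of follow-up.
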